IB	Investigator's Brochure
ICF	Informed Consent Form
ICH	International Conference on Harmonization
ICMJE	International Committee of Medical Journal Editors
LMWH	Low Molecular Weight Heparin
MCP-1	Monocyte Chemoattractant Protein -1
MOP	Manual of Procedures
N	Number (typically refers to Participants)
NEJM	New England Journal of Medicine
OHRI	Ottawa Hospital Research Institute
OHSNREB	Ottawa Health Research Science Network Research Ethics Board
PAD	Peripheral Arterial Disease
PI	Principal Investigator
PTA	Percutaneous Transluminal Angioplasty
QI	Qualified Investigator
QA	Quality Assurance
QC	Quality Control
SAE	Serious Adverse Event/Serious Adverse Experience
SMC	Smooth Muscle Cells
SOP	Standard Operating Procedure
TCPs	Tri-Council Policy Statement
TLR	Target Lesion Revascularization
TNF	Tumor Necrosis Factor
TVR	Target Vessel Revascularization
UFH	Unfractionated Heparin
ULN	Upper Limit of Normal

PROTOCOL SYNOPSIS

Title:	A Phase 2, open label, pilot study to examine the use of Rivaroxaban plus Aspirin vs clopidogrel plus Aspirin for the Prevention of Restenosis after Infrainguinal Percutaneous Transluminal Angioplasty for Critical Limb Ischemia
Short Title:	The RIFLE study
Clinical Trial Phase:	Phase 2
Sponsor:	OHRI
Principal Investigator:	[name] & [name]
Indication:	Patients with Peripheral Artery Disease (PAD) requiring clopidogrel and aspirin following angioplasty
Objectives:	The aim of the trial is to measure the number of relevant clinical outcomes comparing Rivaroxaban plus Aspirin to clopidogrel plus aspirin in patients treated for CLI following PTA, to inform a large scale randomized controlled study.
Duration:	It is expected to take 12 months to enroll 40 participants. Each participant will be in the study for 12 months. The entire trial should be completed in 24 months.
Design:	This is a pilot study conducted at one center, The Ottawa Hospital. It is a Phase 2 open label randomized controlled trial. Consenting participants, meeting all eligibility criteria will be randomized, post PTA procedure, to one of two groups: Rivaroxaban 2.5 mg BID X 90 days plus ASA 81 mg daily OR Clopidogrel 75 mg daily X 90 days plus ASA 81 mg daily Participants will have study drug dispensed at Day 1 and take medication for 90 days. ASA may be continued after the study, for both groups, as per the standard of care. Visits will occur at 7 days, 30 days, 90 days, 6 months and 12 months. Participants will be followed for 12 months (\pm 14 days) in total. Adverse events will be collected for the first 90 days .
Intervention Description:	Treatment Arm 1 Rivaroxaban 2.5 mg twice daily for 90 days (rivaroxaban will be started 6 to 8 hours after the finalization of the procedure) and 325mg of ASA on day 1 then 81 mg of ASA daily for 89 days Treatment Arm 2 Clopidogrel 300mg on Day 1 (loading dose) then 75 mg daily for 89 days and 325mg of ASA on Day 1, then 81 mg of ASA daily for 89 days
Number of participants:	40


Inclusion and Exclusion Criteria
	
Inclusion Criteria:
 
 1. Written informed consent and able to comply with protocol. 2. Infra-inguinal PAD presenting as CLI with Rutherford category ≥ 1. 3. More than 50% stenosis in the target infrainguinal vessel. 4. Good candidates for PTA using POBA (plain old balloon angioplasty) with or without stenting defined as TASC a, b, c and d lesions 
Exclusion Criteria:
 
 1. Acute limb-threatening ischemia (e.g. embolic disease) 2. Hybrid procedures 3. Creatinine clearance < 30 mL/min 4. Platelet count $< 100 \times 10^9/L$; Hbg < 100 g/L 5. INR > 1.5; 6. History of or condition associated with increased bleeding risk including, but not limited to: 
 a) Major surgical procedure or trauma within 30 days before the randomization visit b) Clinically significant gastrointestinal bleeding within 6 months before the randomization visit c) History of intracranial, intraocular, spinal, or atraumatic intra-articular bleeding d) Chronic hemorrhagic disorder e) Known intracranial neoplasm, arteriovenous malformation, or aneurysm f) Sustained uncontrolled hypertension: systolic blood pressure ≥ 180 mmHg or diastolic blood pressure ≥ 100 mmHg 7. Severe, disabling stroke (modified Rankin score of 4 to 5, inclusive) within 3 months or any stroke within 14 days before the randomization visit 8. Aspirin in combination with thienopyridines within 5 days before randomization 9. Intravenous antiplatelets within 5 days before randomization 10. Fibrinolytics within 10 days before randomization 11. Known significant liver disease (e.g., acute clinical hepatitis, chronic active hepatitis, cirrhosis or ALT > 3ULN) 12. Childbearing potential without proper contraceptive measures, pregnancy or breast feeding 13. Drug addiction or alcohol abuse within 12 months before the randomization visit 14. Systemic treatment with strong CYP 3A4 and P-glycoprotein inhibitors : such as ketoconazole, itraconazole, posaconazole, or ritonavir 15. Known allergy or hypersensitivity to any component of rivaroxaban, ASA or clopidogrel 16. Need for long term anticoagulation or double antiplatelet agents for reasons other than PAD such as atrial fibrillation, heart valve replacement, acute coronary syndrome, stroke or venous thromboembolism 17. Anticipated need for chronic (> 4 weeks) therapy with non-steroidal anti-inflammatory drugs. 18. Concomitant treatment with any other anticoagulant, including oral anticoagulants, such as warfarin, dabigatran, apixaban, except under circumstances of switching therapy to or from study treatment. 19. Severe concomitant condition or disease (e.g. life expectancy < 6 months secondary to cancer, advanced liver disease or dementia)
--	---

1 STUDY RATIONALE AND BACKGROUND

1.1 CRITICAL LIMB ISCHEMIA (CLI)

Peripheral arterial disease (PAD) affects over 27 million people in the industrialized world, and is associated with significant morbidity and mortality¹. Up to 10% of patients with PAD² will develop critical limb ischemia (CLI) presenting as resting pain, ulcers, gangrene, and limb loss^{1;3;4}. The typical prognosis of CLI is poor. Within 3 months of onset, 12% of patients will require an amputation and 9% will die; by one year the mortality rate is 22%². With rates surpassing those of patients with coronary artery disease (CAD), patients with CLI are also at high risk of stroke, acute coronary syndrome (ACS), and cardiovascular (CV) death^{5;6}.

Treatment goals for CLI are to preserve life and limb; maintain function; relieve pain; and minimize the frequency and magnitude of repeated interventions^{7;8}. Percutaneous transluminal angioplasty (PTA) procedures have revolutionized the management of patients with peripheral vascular disease and critical limb ischemia, providing a minimally invasive alternative to open bypass surgery in what is typically an elderly population with multiple co-morbidities and with limited life expectancy⁸. In addition, PTA has enabled treatment to be on an outpatient basis at a relatively low cost, and thus a low overall burden to the health care system. In the United States⁹ the use of endovascular interventions grew substantially between 1996 and 2006, while bypass surgery decreased by 42%. Unfortunately, durability of these procedures is countered by restenosis and re-occlusions within the treated segment, ranging from ~40-60% primary patency rates at 1 year. Restenosis of the treated arterial segment is a major multi-factorial clinical problem following a PTA in patients with CLI, especially in those affected with infra-inguinal disease^{2;10;11}. Acute restenosis of the treated segment (<4 weeks post-PTA) is secondary to platelet and coagulation system activation whereas late restenosis is usually associated with myointimal proliferation, negative remodeling, and arterial recoil a process starting as early as 5 days post procedure¹¹. In order to prevent early re-thrombosis, restenosis, and cardiovascular events, most guidelines agree that aspirin (ASA) or ASA-clopidogrel should be given to all patients undergoing PTA^{7;12}. Based on the findings of the CHARISMA trial¹³ (which suggest that patients with symptomatic PAD would benefit from the combination of ASA plus antiplatelet compared to ASA alone) and studies of post coronary PTA supporting the superiority of ASA-clopidogrel¹⁴, the general consensus is that post lower limb PTA patients should receive ASA-clopidogrel over ASA alone^{7;8}. According to a recent survey we conducted, in Canada, 44.6% of vascular surgeons use ASA-clopidogrel, 27.6% use ASA alone, and 23.4% use clopidogrel alone.

1.2 ROLE OF ANTICOAGULATION IN CLI PATIENTS TREATED WITH PTA

Although not fully understood, the complex pathogenesis of restenosis is most likely caused by one or more of the following: Platelet activation and aggregation, mural thrombus, myointimal hyperplasia. Active thrombin remains abundant in mural thrombi following PTA and may be important for vessel repair processes¹⁵ as it directly stimulates vascular smooth muscle cell (SMC) proliferation and migration¹⁵ via interaction and proteolytic activation of its direct cellular targets (PAR-1, 3, and 4). In animal models direct thrombin inhibition reduces atherosclerosis progression, promotes plaque stability, and reduces restenosis in rabbits with atherosclerosis after PTA. Compared to healthy controls, patients with PAD, especially those with CLI, have higher levels of circulating D-dimers and thrombin-AT complex suggesting a prothrombotic state^{15;16}, especially after a PTA. This prothrombotic state could have important prognostic implications. Namely, in patients with ACS, elevations of D-dimers are associated with higher risk of cardiovascular death, myocardial infarction, stroke and stent thrombosis^{17;18}. Treatment with ASA¹⁹ or clopidogrel²⁰ does

not reduce D-dimers levels, but the use of anticoagulant drugs has shown to reduce D-dimers and thrombin fragment levels¹⁹. Anticoagulant drugs are not usually recommended for the prevention of restenosis and vascular events following PTA for PAD^{12,21} but small studies have suggested that anticoagulation with LMWH given to either surgical²² or PTA²³⁻²⁷ treated CLI patients improve restenosis rates in comparison to ASA, and also improve ulcer healing^{28,29}. LMWHs produce their major anticoagulant effect by catalyzing antithrombin-mediated inhibition of coagulation factors. In addition to the antithrombotic properties, LMWH have SMC antiproliferative effects^{19;30;31}; which could explain the benefits of anticoagulation in patients with CLI requiring PTA¹⁸. Although, the effects of LMWH on smooth muscle activation are not clearly understood, recent evidence has suggested that LMWH upregulates CD44 expression³² leading to an antiproliferative function mediated by differential activation of ERK and Rac genes³³. A recent randomized trial demonstrated that ERK 1/2 activation (a surrogate marker of smooth muscle cell proliferation) was increased post-PTA in patients with CLI and that the combination ASA-clopidogrel has no effects on its expression³⁰ thereby supporting the hypothesis that the use of anticoagulant drugs could be beneficial after PTA.

1.3 DIRECT FACTOR XA INHIBITORS IN PAD

Direct FXa inhibitors, such as rivaroxaban, are oral agents that inhibit factor Xa leading to a decrease in thrombin formation and potentially, a decrease in platelet activation. Rivaroxaban is detected 2–4 hours after oral administration, has half-life of 7 to 11 hours, and is associated with few drug interactions³⁴. In phase III randomized trials; rivaroxaban and apixaban have shown to be effective for stroke prevention in patients with AFIB^{35,36}; DVT prevention after surgery³⁷⁻³⁹; and treatment of VTE⁴⁰⁻⁴². In patients with ACS⁴³, rivaroxaban reduced mortality, ACS, stroke, and stent thrombosis, although, along with these benefits is an increased risk of major bleeding⁴³. It is widely believed that activated FXa has limited functions other than serving as the principal mediator of thrombin generation from prothrombin via the prothrombinase complex⁴⁴. Factor Xa occupies a critical juncture in the coagulation cascade⁴⁵ and controls thrombin generation. The activation of one molecule of FXa results in the generation of 1000 molecules of FIIa⁴⁶. FXa initiates intracellular signaling in various cell types of the cardiovascular system, preferentially mediated via PAR-2⁴⁷ which contributes to the production of proinflammatory cytokines, tissue factor up-regulation, SMC proliferation, and the release of vascular endothelial growth factor. Inhibition of FXa prevents thrombin generation via inhibition of free, prothrombinase-bound, and clot-associated Factor Xa and consequently attenuates thrombus-associated procoagulant activity³⁴. This explains why compared to heparin, that allows persistent thrombin generation and direct thrombin inhibitors that aggravate thrombin generation, direct FXa inhibitors allow for small amounts of thrombin generation and protein C activation. The potential effects of FXa inhibition for the prevention of restenosis following PTA could be caused by the reduction of clot-induced mitogenesis and inflammatory gene expression in human vascular SMC⁴⁸; inhibition of the procoagulant activity of activated monocytes and macrophages⁴⁹; and effects on the intrinsic coagulation pathways. To our knowledge only one study conducted in healthy volunteers suggested that rivaroxaban reduced thrombus associated mitosis of SMC of the aortic arch⁴⁸. In animal models, vascular remodeling and myointimal formation were reduced on targeted delivery of nonspecific factor Xa inhibitors^{34;44;50-52}. Animal models have suggested that rivaroxaban decreases mRNA expression of inflammatory mediators, such of IL-6, TNF- α , MCP-1, and Egr-1 promoting arterial plaque stability. In stent thrombosis models, rivaroxaban either alone or in combination with ASA+/-clopidogrel initiated a dose-dependent inhibition of FXa-induced, tissue factor-induced, thrombin-induced platelet aggregation, and ADP-induced platelet aggregation⁵³. In conclusion, evidence suggests that

inhibition of Factor Xa with rivaroxaban could reduce major vascular outcomes and thrombin associated SMC proliferation leading to restenosis after PTA for CLI²⁴.

1.4 RATIONALE FOR TREATMENT SCHEDULES

We selected rivaroxaban 2.5mg twice daily because:

1. Rivaroxaban is the only FXa inhibitor that has shown to improve cardio-vascular outcomes in patients with¹ and without ACS^{2, 3}; furthermore, it has shown to reduce systemic non-CNS systemic⁴ embolism and stent thrombosis post PTA⁵.
2. A 2.5 mg twice daily dose appears to provide the best risk/ratio in combination with antiplatelet agents for the prevention of vascular events in patients treated with antiplatelet agents. The risk of bleeding in patients receiving rivaroxaban and antiplatelet appears to be increased regardless of the treatment indication. Mega et al suggested that a 10 mg daily dose of Rivaroxaban in combination with aspirin was associated with a 2.2% risk of TIMI major bleeding whereas it was 0% in those treated with a 5 mg daily dose plus aspirin. In participants treated with a total daily dose 5 mg of rivaroxaban, those who received 2.5 mg twice daily had a lower bleeding risk than those treated with 5 mg once daily (1.4 vs. 2.9%); furthermore twice daily dosing was associated with a lower number of cardiovascular events (6.6 vs. 9.4%)(6). In ATLAS ACS 2–TIMI 51, the 2.5-mg twice-daily dose of rivaroxaban compared with placebo was associated with reductions of 34% for cardiovascular death and 32% for all-cause death, which were not seen with the 5-mg twice-daily dose(1).
3. Although previous studies looking at the role of anticoagulation post PTA for CLI have used prophylactic doses of LMWH(7), our concern is that patients with CLI are older and sicker and a dose of rivaroxaban of 10 mg once daily in combination with aspirin will be associated with a higher bleeding risk without significant improvement in outcomes.

We selected ASA-clopidogrel as comparator because it is the treatment recommended by guidelines^{7,8}, and is used by 50% of vascular surgeons in Canada

Since optimal medical management to decrease restenosis and thrombosis rates following PTA would make an important contribution to the sustained success of endovascular treatment, the proposed study will evaluate indicators of the effect of rivaroxaban in patients with CLI requiring PTA.

2 HYPOTHESIS

We hypothesize that the addition of rivaroxaban to antiplatelet agents (ASA) following PTA will lead to a reduction in the rate of any/all of the following: restenosis, amputation, and/or major cardiovascular events in patients with CLI, as compared to the treatment of clopidogrel plus ASA.

3 STUDY OBJECTIVE

The aim of the trial is to establish if the use of rivaroxaban 2.5 mg twice a day plus ASA would improve relevant clinical outcomes, as compared to dual antiplatelet agents in patients treated with CLI following PTA. The data from this pilot trial will inform us if a multi center, large scale, randomized trial is warranted.

4 STUDY DESIGN

This is an open label single center randomized controlled pilot study.

4.1 INCLUSION CRITERIA:

1. Written informed consent and able to comply with protocol.
2. Infra-inguinal PAD presenting as CLI defined with Rutherford category of ≥ 1 .
3. More than 50% stenosis in the target infrainguinal vessel
4. Participant must be a good candidate for PTA using POBA (plain old balloon angioplasty) with or without stenting defined as TASC a, b, c and d lesions.

4.2 EXCLUSION CRITERIA:

1. Acute limb-threatening ischemia (e.g. embolic disease)
2. Hybrid procedures
3. Creatinine clearance <30 mL/min
4. Platelet count $<100 \times 10^9/L$; Hbg < 100 g/L.
5. INR >1.5
6. History of or condition associated with increased bleeding risk including, but not limited to:
 - a. Major surgical procedure or trauma within 30 days before the randomization visit
 - b. Clinically significant gastrointestinal bleeding within 6 months before the randomization visit
 - c. History of intracranial, intraocular, spinal, or atraumatic intra-articular bleeding
 - d. Chronic hemorrhagic disorder
 - e. Known intracranial neoplasm, arteriovenous malformation, or aneurysm
 - f. Sustained uncontrolled hypertension: systolic blood pressure ≥ 180 mmHg or diastolic blood pressure ≥ 100 mmHg
7. Severe, disabling stroke (modified Rankin score of 4 to 5, inclusive) within 3 months or any stroke within 14 days before the randomization visit
8. Aspirin in combination with thienopyridines within 5 days before randomization
9. Intravenous antiplatelets within 5 days before randomization
10. Fibrinolytics within 10 days before randomization
11. Known significant liver disease (e.g., acute clinical hepatitis, chronic active hepatitis, cirrhosis or ALT >3 ULN)
12. Childbearing potential without proper contraceptive measures, pregnancy or breast feeding*
13. Drug addiction or alcohol abuse within 12 months before the randomization visit
14. Systemic treatment with strong CYP 3A4 and P-glycoprotein inhibitors : such as ketoconazole, itraconazole, posaconazole, or ritonavir
15. Known allergy or hypersensitivity to any component of rivaroxaban, ASA or clopidogrel
16. Need for long term anticoagulation or double antiplatelet agents for reasons other than PAD such as atrial fibrillation, heart valve replacement, acute coronary syndrome, stroke or venous thromboembolism
17. Anticipated need for chronic (> 4 weeks) therapy with non-steroidal anti-inflammatory drugs.
18. Concomitant treatment with any other anticoagulant, including oral anticoagulants, such as warfarin, dabigatran, apixaban, except under circumstances of switching therapy to or from study treatment.

19. Severe concomitant condition or disease (e.g. life expectancy <6 months secondary to cancer, advanced liver disease or dementia)

* Sexually active women of child bearing potential must undergo a serum pregnancy test ((β -HCG) before study entry and use highly effective methods of contraception. These may include: hormonal contraceptives (e.g. combined oral contraceptives, patch, vaginal ring, injectables, and implants); intrauterine device (IUD) or intrauterine system (IUS); vasectomy and tubal ligation. Highly effective methods of contraception might not always be achievable in the clinical trial setting and, therefore, the most effective alternative can be achieved using methods in combination.

The "**double barrier**" methods of contraception (e.g. male condom with diaphragm, male condom with cervical cap) can be used as an effective alternative to the highly effective contraception methods described above. The use of a male condom in association with spermicide should not be considered a suitable double barrier method for contraception.

5 STUDY MEDICATION

5.1 SCREENING MEDICATION/STANDARD OF CARE

Participants will be screened within 30 days prior to the PTA procedure. All participants enrolled in the study will receive a loading dose of 325 mg of ASA and IV heparin as per the TOH protocol during the procedure. The 325mg loading dose of ASA will be considered and recorded as the day 1 dose of ASA.

5.2 RANDOMIZATION

Participants will only be randomized once the surgeon has completed the PTA +/- stent . PTA will be considered successful once the target lesion is crossed with a wire and catheter and a balloon angioplasty has been successfully performed. Randomization will be conducted using a customized web-based program developed for this study. The randomization process will be initiated by the local study coordinator who will access the web-based system and enter the patient's unique identifier and confirmation of eligibility and informed consent. Specific patient allocation will then be electronically delivered, to the research pharmacy who will prepare and dispense trial medication.

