6.2 SCREENING (-30 DAYS TO -1 DAY OF PTA)

Participants will be screened within 30 days of the PTA procedure.

The following will occur at the screening visit:

- Physical examination (Height and Weight plus BMI)
- Demographics (age, gender, race)
- Tobacco use
- Medical History including:
 - Bleeding history
 - History of stroke, TIA, CAD, CKD, COPD, Hypercholesterolemia
 - History of acute coronary syndrome
- Medication history
- Previous tissue loss
- Co-morbidities including
 - Exclusion criteria
 - Hypertension
 - Obesity
 - Diabetes
- Disease severity (Rutherford scale) and ABI index from medical record

- Anatomic level of disease⁵⁶.
- Obtain bloodwork results for CBC, coagulation tests (INR, PTT), and serum creatinine

6.2.1 Study Day 1: PTA, Randomization/Treatment Day 1

All participants enrolled in the study will receive a loading dose of 325 mg of ASA and IV heparin as per TOH protocol prior to the procedure.

Once the surgeon has completed the PTA +/- stent, participants will be randomized using a web-based program as per section 5.2. Participants will receive study medication as per section 5.3.1 and 5.3.2 for the group to which they are allocated.

At randomization the research coordinator will provide the appropriate training for each participant on:

- Monitoring of outcome events and adverse events.
- Review signs and symptoms of bleeding and provide instructions and study contact numbers.
- Details of the study requirements (follow-up schedule) and the importance of follow-up
- Storage and administration of study drug
- How to complete the Medication Diary

Data collected at Day 1 :

- Vascular access specifications: Access routes, size of introducer sheaths used, specifications of device used (length and diameters of balloons/devices implanted)
- Device to artery ratio for balloons and implants, length of treated segment
- Immediate procedural outcome
- Bleeding (approximate blood loss)
- Concomitant medications
- Blood collection (stored for future evaluation of platelet activation , coagulation markers. smooth muscle activation markers and inflammation markers)

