8.2 SAMPLE SIZE CALCULATION

Based on recent data published by Conte et al² we expect that during 1 year of follow up, 54% of participants will experience the primary outcome. A total sample of 40 participants was selected and is within the recommended approach for pilot studies evaluating effects when no prior information upon which to base the sample size is available. This sample size will allow us to detect an absolute 20% reduction in the main clinical outcome with a single sided alpha of 0.2 and power of 0.6 as recommended for pilots studies⁵⁹⁻⁶¹. The study will be considered successful if we can demonstrate a reduction in events in the intervention group supported by changes in biomarkers levels (biological plausibility).

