8.3 STATISTICAL ANALYSIS

All the continuous outcomes will be evaluated with the paired T-test or Wilcoxon-rank sum; proportions will be evaluated using the Fisher's exact test.

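### No stratification or adjustment for baseline Rutherford category is specified, so a chance severity imbalance between two small arms could shift the observed RAS difference by several points

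*Combined protocol and SAP*

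**What the plan says.** Participants "will be randomized, post PTA procedure, to one of two groups" (synopsis, Design). Section 5.2 adds: "Randomization will be conducted using a customized web-based program developed for this study". It lists what the coordinator enters: the participant's identifier and confirmation of eligibility and consent. No allocation ratio, block size, stratification factor or minimisation is given anywhere.

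For binary outcomes, section 8.3 says only that "proportions will be evaluated using the Fisher's exact test". No covariate or stratified analysis is described.

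Section 4.1 and the synopsis require critical limb ischemia (CLI) with Rutherford category 1 or higher. On the scale in section 6.3.1 that runs from mild claudication (1) to severe ulceration or gangrene (6). Section 1.1, by contrast, describes CLI by rest pain, ulcers and gangrene, which are stages 4 to 6 on that scale.

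Baseline severity is collected. Section 6.2 lists "Disease severity (Rutherford scale) and ABI index from medical record" at screening. Sections 9.4 and 9.5.1 have baseline comparability reported to the DSMB, but no analysis step follows if the arms differ.

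The size assumptions are in section 8.2: "A total sample of 40 participants was selected", "54% of participants will experience the primary outcome", an "absolute 20% reduction in the main clinical outcome", and a "single sided alpha of 0.2 and power of 0.6". The same section counts the study as successful if events are fewer in the intervention arm and biomarkers support this.

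**The concern.** Read literally, eligibility mixes claudicants with patients who have tissue loss. Section 1.1 ties CLI to early amputation (12% within 3 months), and above-ankle amputation is a component of RAS, so severity may well be prognostic for the primary outcome. With about 20 participants per arm, simple chance can leave one arm noticeably sicker. Because section 8.2 judges success on the observed reduction in one sample of 40, a shift caused by severity feeds into that judgement, and the planned test cannot remove it.

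Secondary outcome 1 has a separate, mechanical dependence on baseline. It requires improvement by 2 Rutherford classes. A category 1 participant can fall only to stage 0, which is 1 class, and so can never be a responder.

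**Working it through.** **Inputs.** From section 8.2: N = 40, control rate 0.54, target rate 0.54 − 0.20 = 0.34, one-sided alpha 0.2, stated power 0.6. Assumed, because the documents do not say: 1:1 allocation (20 per arm), a split at Rutherford 1–3 versus 4–6, the share in 4–6, and the gap in RAS risk between the two groups.

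**1. The plan's own figure.** Pooled z-test, 20 per arm:
- Mean rate 0.44. Null SE = √(2 × 0.44 × 0.56 / 20) = 0.157. Alternative SE = √(0.54 × 0.46/20 + 0.34 × 0.66/20) = 0.154.
- Power = Φ[(0.20 − 0.842 × 0.157)/0.154] = Φ(0.44) = 67.1%.
- Exact enumeration of the planned one-sided Fisher test gives 56.9%, and a continuity-corrected z-test 54.6%.

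The stated 60% lies between these but matches none of them. It is used here only as a reference point.

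**2. Chance of imbalance.** Let K of 40 be in category 4–6 and x of them fall in one arm. Then P(x) = C(K,x) C(40−K,20−x) / C(40,20), and the difference in shares is |2x − K|/20.
- For K = 20, a difference under 20 points needs x = 9, 10 or 11. P(10) = 0.2476 and P(9) = P(11) = 0.2047. So P(≥ 20 points) = 1 − (0.2476 + 2 × 0.2047) = 34.3%, or 17.2% in one given direction.
- K = 12 or 28: 30.1%. K = 8 or 32: 23.5%.
- Odd K gives less, because the next possible difference is 25 points: at most 20.5% (K = 19 or 21), and 12.7% at K = 9.
- If the severe count in each arm is binomial, 16% to 27% for a severe share of 20% to 80%. Under simple randomization, 19% to 27% for K = 12, 20 or 28.

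A fair summary is 1 in 5 to 1 in 3 for middling mixes, and less when one group is rare.

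**3. Effect on the RAS difference.** Each arm's rate is (low risk) + gap × (share in 4–6), so the shift equals gap × imbalance. For a 20-point imbalance:

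| Assumed risk gap | Shift | Imbalance needed for a 20-point shift | Its probability at K = 20 |
|---|---|---|---|
| 20 points | 4 points | 100 points | about 0 |
| 30 points | 6 points | 67 points | about 0 |
| 40 points | 8 points | 50 points | 0.4% |
| 50 points | 10 points | 40 points | 2.6% |

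**4. Error rates of one-sided Fisher at 0.2, no treatment effect, mean rate 54%.**
- Averaged over randomization: 13.3%, below the nominal 20%.
- Given 12 severe in control and 8 in treatment: 22%, 26% and 29% for gaps of 30, 40 and 50 points.
- Given 10 and 10: 12%, 11% and 10%.
- Given 8 in control and 12 in treatment: 6%, 4% and 2%.

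**5. After stratifying.** Simulated blocks of 4 within two strata, with 50% severe, gave no imbalance of 20 points or more in 40,000 runs; 1.4% reached 10 points, the maximum. On the normal approximation, power is 69% to 72% for gaps of 20 to 40 points, against 67% to 68% unstratified. Enumerating an exact stratified test (10 from each group per arm, a 20-point reduction in both groups) gives 57.0%, 57.2%, 57.7% and 59.3% for gaps of 20, 30, 40 and 50 points, against 56.9% for Fisher. The power gain is close to nil unless the gap is very large.

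**The case against.** The strongest case against is that randomization already accounts for chance imbalance. Step 4 confirms it: the planned test stays within its level on average. A reader might infer that the unadjusted Fisher test is invalid or inflates type I error, and the documents do not support that. Only the error rate conditional on an observed imbalance rises.

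A reader might also infer that an imbalance as large as the treatment effect is likely. It is not. Even the most unfavourable mix gives about 1 in 3, and 20 points of imbalance in a covariate is not 20 points in the outcome. Nor does section 8.2 set a 20-point threshold for success. That figure is the detectable difference, and section 9.3 has the Steering Committee weigh the various outcomes.

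The risk gap is assumed. RAS also includes reintervention and restenosis defined by ABI or imaging, and nothing in the documents says that these vary by Rutherford category. Other factors (TASC class, stenting, diabetes) could be argued for, and a pilot of 40 can carry few strata. Stratification is also unstated rather than excluded, so the program might include it.

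Two objections narrow the remedy. If the CLI wording governs entry, the 1–3 stratum would be nearly empty. And a 1–3 versus 4–6 split does not balance category 1, the only category that cannot improve by 2 classes. These points limit the size of the concern and shape the fix. They do not remove the gain in balance, which costs little because the variable is already collected.

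**Conclusion.** The point holds as a modest, inexpensive improvement rather than an error that undermines the trial. The documents specify neither stratification nor adjustment for a recorded baseline variable that spans six categories as eligibility is written. With 20 per arm, a 20-point severity imbalance has roughly a 1-in-5 to 1-in-3 chance and would shift the RAS difference by about 4 to 10 points, which is 20% to 50% of the 20-point design difference. This rests on an assumed severity mix and assumed risk gaps of 20 to 50 points. The case for acting is protection of the observed reduction against a bad draw, not power and not the overall error rate. If only stages 4 to 6 in fact enter, the severity spread is narrower and this split adds little.

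**What to change.** 1. Reconcile the CLI wording with the Rutherford threshold across the synopsis and sections 1.1, 4.1 and 6.3.1 before fixing the cut-point.
2. In section 5.2, state the allocation ratio. Add Rutherford 1–3 versus 4–6 (or the cut-point that suits the reconciled criteria) as the single stratification factor, with random block sizes. Use the screening value, since randomization follows the procedure.
3. In section 8.3, make the main RAS analysis a Mantel-Haenszel risk difference with an exact stratified test on the same factor. Keep Fisher's test as a sensitivity analysis.
4. Report secondary outcome 1 by baseline category, and show how many category 1 participants are in each arm.
5. If recruitment has begun, leave allocation alone and prespecify only the analysis changes, before outcome data are compared by arm.

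The cost is one field in the allocation program and a few sentences of analysis text, with no new measurement. The downside is two small strata, and an exact test that may be slightly more conservative if category turns out not to be prognostic.
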